## **VIII. Risks and Discomforts**

We anticipate the major risks due to PrEPsteps are the potential for exposure to metal components in the digital pill, retention of the radiofrequency emitter portion of the digital pill, and allergic reaction to the silver and zinc components of the radiofrequency transmitter and to the gelatin pill capsule. Participants may also experience psychological discomfort in working with study staff to program PrEPsteps, and a risk of discoverability of their involvement in the study from PrEPsteps. Major psychological discomforts could occur during study interviews when participants are asked about their adherence patterns. We have addressed each of these risks below:

**Exposure to Metal Components in Digital Pill:** The Digital Pill is manufactured from the same basic components as other ingestible medical devices. The radiofrequency tags contain minimal amounts of silver, zinc and magnesium that are significantly less than the recommended daily intake of these metals. In order to prevent absorption of these metals, the radiofrequency tag is coated with an epoxy and ethylcellulose coating in a technique that is used for other ingestible medical devices. Extensive experience in the use of ingestible small bowel endoscopy cameras has not reported adverse events related to the exposure of electronic components.

**Digital Pill Radiofrequency Emitter Retention:** Study participants may experience retention of the radiofrequency emitting portion of the digital pill. A study assessing the efficacy of the capsule portion of PrEPsteps among healthy volunteers documented 560 successful ingestion events without any adverse effects. [name] has completed a pilot study that recorded 96 ingestions with the digital pill containing oxycodone without any adverse events. Additional pilot data from Novartis of over 100 participants who ingested radiofrequency tagged gelatin capsules revealed no reports of sensor retention (Personal communication from [name], Novartis). An additional investigation to determine the safety of digital pills demonstrated no retention of any of the components of the digital pill by abdominal imaging. The best comparison to the digital pill are capsule endoscopy pills which are over twice the size of digital pills. Over a decade of experience of capsule endoscopy has revealed a capsule retention rate of less than 2%. In the case of a retained endoscopy pill, patients were mostly asymptomatic, and treatment consisted only of oral fluid administration. Patients who elected to have the capsule removed successfully underwent elective partial small bowel resection with pathologic findings including mild bowel stricture or intimal ulceration from capsule retention. Complication rates among patients with Crohn's disease, bowel neoplasm, radiation enteritis, or stricture were higher. In high-risk patients, standard therapy for retained endoscopy pills included aggressive oral hydration with successful removal of the retained pill. We believe that the risk of retention of a PrEPsteps capsule will be less than that of a capsule endoscopy pill given the smaller dimensions of the digital pill. Unlike a capsule endoscopy pill, PrEPsteps is dissolvable with only the radiofrequency emitting portion of the capsule passing through the gastrointestinal tract. In order to minimize the risk of PrEPsteps capsule retention, we plan to exclude patients with underlying bowel disease or surgical intervention to the bowel.

**Allergic Reaction:** There is a risk of allergic reaction to the silver and zinc components of the radiofrequency transmitter, and to the gelatin pill capsule used to encase the radiofrequency transmitter and PrEP inside the capsule. In order to minimize the risk of a potential allergic reaction, we plan to exclude patients with a known allergy to silver, zinc or gelatin.

**Risk of Discoverability from PrEPsteps:** There is a risk of discoverability of PrEP use or participation in the study in the case when a study participant's messages from the PrEPsteps app is discovered by a bystander, or if PrEPsteps messages are discovered by individuals outside of the study. We will take 4 major steps to ensure that we maximally protect participants from the risk of discoverability.

- *Password protection on participants' cellphones:* We will ensure that participants' cellphones are enabled with password protection (or Touch ID, for iPhones). Participants will be the only individuals who have access to their personal cellphones.
- *Messaging that does not directly reveal PrEP ingestion:* During focus groups in aim 1, we will craft messages from PrEPsteps that avoid inadvertent disclosure that participants are on PrEP to protect against individuals who are uninvolved in the study reading messages from PrEPsteps. Although messages are password protected, we will take the additional step of ensuring the text of messaging protects participants against PrEP discoverability.
- *Masking the icon of the PrEPsteps app to prevent discoverability:* We will mask the icon of the PrEPsteps app as a generic "ID Cap" app to avoid discoverability of PrEP ingestion or participation in PrEPsteps.
- *Opaque digital pill capsules:* The digital pill gelatin capsule is opaque, prevent discoverability of PrEP ingestion by recognition of the color of TDF/FTC.

**Psychological Discomfort of Disclosing Adherence Patterns:** Participants may experience psychological discomfort in disclosing and learning of their adherence data during study visits.

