**IV. Subject Selection**

Inclusion Criteria	Exclusion Criteria
Aim 1: 
 
1) Cis-gender MSM with problematic stimulant use (identified in medical record as stimulant dependence or recurrent stimulant use that interferes with daily life: ICD 304, 305 and 292) or self-report (e.g. reported stimulant use in the past 6 months)
 
2) HIV-negative
 
3) On PrEP or qualifies for PrEP
 
4) Age 18 or older
 
	Aim 1: Does not speak English
Aim 2: 
 
1) Cis-gender MSM with moderate to severe non-alcohol substance use disorder (via MINI assessment)
 
2) HIV-negative
 
3) On PrEP or initiating PrEP
 
4) Has qualifying laboratory testing: Cr clearance, HBV, liver function tests
 
5) Owns a smartphone with Android or iOS
 
6) Age 18 or older
 
	Aim 2: 
 
1) Does not speak English
 
2) HIV positive
 
3) History of Crohn's disease or ulcerative colitis
 
4) History of gastric bypass, bowel stricture
 
5) History of GI malignancy or radiation to abdomen
 
6) Unable/unwilling to ingest digital pill
 
7) Allergy to gelatin, silver or zinc (components of the digital pill)
 
8) Does not qualify for PrEP (abnormal liver function, or Cr Clearance <60)
 

Aim 3: Participants in Aim 2 will be enrolled in Aim 3	Aim 3: Did not participate in Aim 2

*Justification for Inclusion Criteria*

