#### *Justification for Exclusion Criteria*

We are excluding individuals with bowel strictures, Crohn's disease, ulcerative colitis, bowel neoplasm or radiation to the abdomen in order to minimize the risk of retention of digital pill components. Despite safety data that has demonstrated no risk of retained components of the digital pill in individuals, potential participants that are at risk of developing bowel stricture or obstruction would be at the highest risk of experiencing adverse events related to the digital pill.

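### Section VIII says patients with prior bowel surgery are excluded, but the Aim 2 exclusion list names only gastric bypass

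*Combined protocol and SAP*

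**What the plan says.** Three places in the combined protocol and SAP describe who is kept out of Aim 2 on bowel grounds. The second copy of the protocol text has the same wording in each.

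- **Section VIII, paragraph on emitter retention.** The stated safeguard is to "exclude patients with underlying bowel disease or surgical intervention to the bowel". The same paragraph reports from capsule endoscopy: "Complication rates among patients with Crohn's disease, bowel neoplasm, radiation enteritis, or stricture were higher".
- **Section IV, Aim 2 exclusion list.** Of eight items, three concern the gut. Item 3 covers Crohn's disease and ulcerative colitis. Item 4 reads "History of gastric bypass, bowel stricture". Item 5 reads "History of GI malignancy or radiation to abdomen".
- **Section IV, Justification for Exclusion Criteria.** It states: "We are excluding individuals with bowel strictures, Crohn's disease, ulcerative colitis, bowel neoplasm or radiation to the abdomen". It names no operation. It adds that people "at risk of developing bowel stricture or obstruction would be at the highest risk of experiencing adverse events related to the digital pill".

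**The concern.** Retention is one of the major risks that Section VIII names, and excluding certain patients is the mitigation it offers. That mitigation exists only so far as the eligibility list carries it out. Section VIII describes a general class, bowel surgery; the list contains one member of that class. An IRB or DSMB member who relies on Section VIII would believe in a protection that screening staff have no criterion to apply.

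At stake are participant safety and the protocol's internal consistency. No statistical result depends on it.

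**Working it through.** The plan gives no figure to reproduce here, so the check is mainly a comparison of texts.

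**Step 1. Set the statements side by side.**

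| Condition | Section VIII safeguard | Section IV justification | Aim 2 list |
|---|---|---|---|
| Crohn's disease, ulcerative colitis | within bowel disease | named | item 3 |
| Stricture | within bowel disease | named | item 4 |
| Abdominal radiation | not in the safeguard sentence | named | item 5 |
| Neoplasm | within bowel disease | bowel neoplasm | item 5, as GI malignancy |
| Gastric bypass | surgical class | not named | item 4 |
| Other bowel surgery | surgical class | not named | **absent** |

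Of the five conditions in the justification, four appear unchanged in the list (stricture, Crohn's disease, ulcerative colitis, radiation) and one is reworded (neoplasm).

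**Step 2. Run a test case.** Take a man with a bowel resection after trauma and no stricture, inflammatory bowel disease, malignancy or radiation. Items 3, 4 and 5 do not apply. The other five items (language, HIV status, ability or willingness to swallow the pill, allergy, fitness for PrEP) do not apply either. He is eligible under the list and excluded under Section VIII. Surgery done for a listed diagnosis, or followed by a known stricture, is already covered.

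**Step 3. Look for another safeguard.** Item 6 requires staff to judge whether someone can or will ingest the pill, but it is not a general safety discretion. The Screening Visit describes consent, laboratory results, the substance use screener, an acute HIV screener and a rapid HIV test. It describes no abdominal imaging or surgical-history step. Even if staff learned of an operation, no criterion would act on it.

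**Step 4. Ask whether such sentences in Section VIII normally match the list.** The allergy paragraph uses the same construction: "we plan to exclude patients with a known allergy to silver, zinc or gelatin". Exclusion 7 lists those same three substances, 3 of 3. This is modest support for reading the surgery sentence as a real exclusion.

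**Step 5. Compare the neoplasm terms.** GI malignancy is wider by site and narrower by type, because it omits benign bowel neoplasm. The two terms select different people, but the difference is mostly wording.

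**Step 6. Size the risk, as far as the documents allow.**

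- Section VIII reports no adverse effects or events in 560 + 96 = 656 counted ingestions, no retention on abdominal imaging, and no sensor retention reported in over 100 participants.
- Assuming n = 100 and complete reporting, zero events gives a one-sided 95% upper limit of 1 − 0.05^(1/100) = 2.95% per participant.
- Retention is below 2% for endoscopy capsules more than twice the size.
- Section VIII does not say that any of these people had prior bowel surgery, so none of these figures measures risk in the group at issue.
- Planned exposure is repeated: a 14-day run-in plus 90 pills is 104 scheduled ingestions per participant.

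**Step 7. Cost in screening.** Extra people needed = 60/(1 − p) − 60, where p is the assumed share of otherwise eligible people newly excluded. The documents give no prevalence.

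| p (assumed) | Extra people |
|---|---|
| 1% | 0.6 |
| 3% | 1.9 |
| 5% | 3.2 |
| 10% | 6.7 |

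**The case against.** The best defence is that the Section VIII sentence is a loose summary. Its first half, on underlying bowel disease, is also a class term; read literally it would exclude every bowel condition, and the list does not attempt that. The justification omits gastric bypass altogether, so the prose is plainly not an exact mirror of the list. The allergy sentence repeats specific items, so it says little about how class terms are used.

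This lowers the weight of the point but does not remove it. Even as a summary, the sentence tells the reader that bowel surgery is screened out, and one named operation does not deliver that.

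A second defence is that the documents' own risk evidence does not single out surgery. This stands. Among the groups with higher capsule-endoscopy complication rates, Section VIII names Crohn's disease, neoplasm, radiation enteritis and stricture, not prior surgery. A reader might infer that people with earlier bowel surgery are known to be at raised risk of retention here; the documents do not show that. It follows that widening the list is not the only acceptable remedy, and narrowing Section VIII would also restore consistency.

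A third defence concerns neoplasm. A reader might infer that the different terms open a safety gap of equal weight. They do not: the list is wider by site, and what remains is benign bowel neoplasm without stricture. Copying the justification's term into a history-based criterion could exclude anyone who has had a benign polyp removed.

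**Conclusion.** Wrong as written, but minor: a matter of eligibility and safety consistency. The Aim 2 list does not carry out the surgical exclusion that Section VIII states, and nothing else in the described screening closes the gap.

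The affected group is people with a bowel operation other than gastric bypass and no listed diagnosis or known stricture. I take it to be small and its absolute risk to be probably low, given the reassuring experience in Section VIII. Both are judgements; the documents give neither the prevalence nor the added risk, so I claim no headcount.

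A reader might also infer that the trial's results are compromised. They are not: no estimand, analysis or sample-size figure depends on this point.

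**What to change.** Make one of two changes, in both copies of the protocol text.

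1. **Preferred: widen the list.** Amend Aim 2 exclusion 4 to cover *gastric bypass or other bowel surgery (for example resection, anastomosis or ostomy), or bowel stricture*, and say whether uncomplicated appendectomy is exempt. Add bowel surgery to the Justification for Exclusion Criteria. The cost is a line in each place and about 1 to 4 more people screened at an assumed 1% to 5%. At an assumed 10%, for instance if appendectomy counts, it is about 7, which is why that rule should be written down.
2. **Alternative: narrow Section VIII.** If the sponsor judges other bowel surgery safe, reword the sentence so that it claims only what the list excludes. This costs one sentence and no screening.

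Separately, as a wording matter, use one neoplasm term in the list, the justification and Section VIII. An example is *GI malignancy or current or obstructing bowel neoplasm*, which leaves people with removed benign polyps eligible.

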## **IX. Potential Benefits**

Participants may indirectly benefit from participation in the study by improving their adherence to PrEP. Interacting and using PrEPsteps may confer some increased adherence among study participants.

## **X. Data Transmission from Digital Pills**

It is important to note that no protected health information flows through ingestion events recorded by the digital pill. There is no medication data that identifies study drug as Truvada, nor personal identifiers within the digital pill system. Ingestion of the digital pill activates a generic radiofrequency signal that is collected by the Reader. The Reader then transmits ingestion data via low energy Bluetooth to the participant's cellular phone. This data is collected by an app housed on the participant's smartphone. Within the app, data is converted to Java Script notation that describes the presence of an ingested medication. This data is transferred to servers at our collaborating industry partner, ectectRx. This data is then stored on a secure server. Access is limited to ectectRx maintenance technicians and the study team. For PrEPSteps interventions and text messages, receipt of digital pill ingestion data is sent to the NOMI dashboard- this dashboard automates the PrEPSteps intervention and pushes messages via SMS text messaging to the participant's phone in response to their ingestion patterns. Study participants are identified on the ectectRx and NOMI dashboard only as study numbers. Their PHI is kept within secure Fenway computers. A secure excel spreadsheet that links study numbers to participant names is kept on desktop computers at Fenway accessible to the PI and study team.

## **XI. Data Monitoring and Quality Assurance**

## Detailed Protocol

### Development of Ingestible Biosensors to Enhance PrEP Adherence in Substance Users (PrEPsteps)

We will review and monitor data from PrEPsteps for each study participant. At each study visit, participants will undergo pill counts to correlate adherence data from PrEPsteps, and calculate the accuracy of the digital pill to measure PrEP adherence. Any discrepancies between the digital pill and pill counts will be addressed in real time at each study visit with the participant. For each participant, we will also review signaling from the digital pill to the Reader with our industry collaborator (etectRx) to ensure there are no errors in data transmission contribution to missed adherence events. If errors occur as a result of data transmission, we will correct the participant's adherence data, and convey these changes to participants' PCP via Mimecast secure email. We will additionally obtain dried blood spot testing at study visits 3 and 4 to confirm adherence (see section V. study procedures)

Recorded interviews: Audio-recorded interviews (Aim 1 and 3) will be transcribed using a HIPAA compliant transcription service (Landmark transcription), and scrubbed of identifiers

Aim 2 QA review: Study investigators will conduct QA review of baseline adherence data after the first 10 participants are enrolled. Additionally, we will review adherence data and interactions with PrEPsteps after the first 10 participants randomize to PrEPsteps. We will similarly conduct QA review after the first 10 participants randomize to treatment as usual. We will continue to conduct subsequent QA reviews in increments of 10 participants enrolled in each arm to ensure fidelity of the study data.

**Data Safety Monitoring Board (DSMB):** Three investigators who are external to the study and external to [name] mentoring team as defined by his NIH K23 award with expertise in PrEP, non-alcohol substance use disorder, technology security and behavioral interventions, will comprise a DSMB for Aim 2 (pilot randomized controlled trial) of the research plan. The DSMB will convene annually during Aim 2. Additionally, the DSMB will meet when N=30 study participants are enrolled in Aim 2. They will review the data, and any potential study related adverse events prior to approving the continuation of recruitment. The responsibilities of the DSMB will include:

- Reviewing the research protocol, consent form, and plans for DSMB.
- Evaluating the progress of the pilot randomized controlled trial: recruitment, retention, data quality, site performance, adverse events.
- Protection of participant safety
- Making recommendations to [name] and the Fenway Institute IRB regarding continuation, termination or modification of the study depending on benefits or adverse events.
- Ensuring the confidentiality of study data.
- Reviewing adverse events.
- Providing annual written reports to [name], and NIH regarding safety concerns, continuation or modification of the research plan.

We will additionally comply with all Fenway regulations regarding reporting of adverse events and ensuring data quality.

**Data Tracking:** Ingestion data will be automatically logged into the web interface hosted by ectectRx with a date/time stamp to ensure accurate record keeping of all data and linking to the results. All data will be securely accessed at Fenway Health.

**Data Entry Process:** Protected health information, including study participant demographics, non-alcohol substance use disorder history, and HIV risk factors will be collected by [name] and the research assistant and entered into REDCap, a secure web application being used for data storage and management. A separate spreadsheet of study participant contact information and a technology log including participant mobile phone number, electronic mail (email) address, identifiers of the Receiver, study smartphone and a log of dispensed digital pills will also be maintained by [name] and the RA. All logs will be stored behind TFI firewall and password protected. Each variable with missing data (such as an interruption between smartphone and sensor) will be identified and a placeholder (“<<-99>>”) entered to connote a missing value. Data from the digital pill is recorded on the ectectRx interface and automatically transferred via a HIPAA-compliant secure link to the adherence interface (NOMI). Ingestion data may potentially require editing if there are transmission failures, errors from the reader device, or manually recorded data from study participants. All of these potential edits will be identified by ectectRx in collaboration with the study team. Edits to data will be agreed upon by both parties and approved by the PI. An audit trail of all potential edits will be maintained. We will additionally comply with Fenway regulations regarding reporting of adverse events and ensuring data quality. Landmark Associates Inc, an external company, will be contracted to transcribe audio-taped exit interviews.

**Data Storage:** Raw ingestion data, transcripts from this study and self-report questionnaires will not be made publicly available. De-identified data may be shared with NIH who is funding the study, as well as industry collaborators ectectRx and NOMI. For future investigations that use de-identified participant data, we will submit IRB protocols detailing the use of this data. Mass General Brigham Dropbox is being used for file storage in the study.

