### Components of PrEPSteps Intervention

(see attached, *PrEPsteps\_Study Messages\_Participants Only*):

Intervention Component	Message Content	Timing of Delivery
Contingent Reinforcement	Standardized “Ingestion detected” message and weekly summary of adherence metrics	Immediately after every digital pill ingestion; once weekly
Corrective Feedback	Standardized “It looks like you missed your medication today. What happened?”	2 hours after dosing window has closed without ingestion event
LifeSteps Booster	Participant-generated interventions during study visit 3, linked to corrective feedback content	Linked with corrective feedback message

**Control Condition:** The control condition will receive the digital pill as a medication adherence monitoring device. Participants will be trained on the digital pill device, operation of the reader and the accompanying app. For individuals in the control arm, they will receive confirmation messages surrounding digital pill ingestion. If participants want to see if they ingested a digital pill, they will be able to query this in the app. Participants will receive weekly adherence metrics (please see attached list of PrEPSteps messaging for both conditions).

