## Detailed Protocol

### Development of Ingestible Biosensors to Enhance PrEP Adherence in Substance Users (PrEPsteps)

PrEPsteps	
 
• Life Steps counseling (remote)
 
• Responses to Life Steps programmed into PrEPsteps (remote or onsite)
 
• Substance use counseling (remote)
 
• Dispense digital pills, technology training, digital pill ingestion (onsite)
 
• Return unused digital pills from prior 14-day period (onsite)
 
• Review of adherence data, discussion surrounding nonadherent events (remote or onsite)
 

Treatment as usual	
 
• Life Steps counseling (remote)
 
• Substance use counseling (remote)
 
• Dispense digital pills, technology training, digital pill ingestion (onsite)
 
• Return unused digital pills from prior 14-day period (onsite)
 
• Review of adherence data, discussion surrounding nonadherent events (remote or onsite)
 

**Study Visit 3:** Procedures for this visit will be conducted onsite at Fenway Health, or partially remote, if necessary, in response to COVID-19. This visit will take place 30 days post-randomization. We will contact participants prior to their appointment via text or phone call to remind them of their visit. We will review the previous 30 days of adherence data over and reconcile discordant or nonadherent events with participants in both study arms. Participants will return any unused digital pills from the prior 30-day period (to be counted by study staff). Participants will additionally undergo a blood draw for dried blood spot (DBS) testing for tenofovir diphosphate (to measure adherence and compare DBS against the digital pill), and a urine drugs of abuse immunoassay assessing non-alcohol substance use. Upon participant request, we will inform them of the results of the urine drugs of abuse screen via phone or in-person. A 60-day supply of Truvada digital pills will be dispensed to participants in both study arms at this visit.

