## PrEPsteps Aim 2 Study Flow

### Onsite & Remote Procedures

## Detailed Protocol

### Development of Ingestible Biosensors to Enhance PrEP Adherence in Substance Users (PrEPsteps)

At the conclusion of this study, we will provide the following avenues in which study participants can continue to access PrEP outside of the study: First, participants can return to their primary care provider and ask them to prescribe PrEP, second, we can refer participants to a provider at Fenway Health to prescribe PrEP and finally, participants can access PrEP through the Brigham and Women's Infectious Disease Clinic.

**Remuneration:** Participants will be remunerated via ClinCards using the following schedule. Participants will only receive compensation for completed study visits. Participants who enrolled prior to the start of the PrEPsteps supplement in September 2022, and who elect to complete the additional questions added to the baseline quantitative assessment, will be compensated an additional \$20.

Study Visit	Compensation
Screening Visit	\$20
Study Visit 1	\$20
Study Visit 2	\$30
Study Visit 3	\$30
Study Visit 4	\$30
Study Visit 5	\$40
Study Visit 6	\$50
Additional Supplement Questions (if applicable)	\$20
Total	\$240

**Participant Contact:** We will contact participants via text message at described times after study visits (see *PrEPsteps Study Messages\_Participant Only*). Additionally, if participants do not respond to text messages (e.g., technology check-ins at days 2, 5, 7, 16, 19, 21), we will contact them via phone, and/or email. We will also contact participants to remind them of upcoming study visits via phone, Nomi text message, patient portal, and/or email. Upon participant request, we will inform them of the results of the urine drugs of abuse screen at study visits 3 and 5 via phone or in-person. As part of the PrEPsteps supplement, questions were added to the baseline quantitative assessment (*PrEPsteps\_Quantitative Assessment\_Visit 1*). The study team will contact participants via phone who completed the Study Visit 1 baseline quantitative assessment prior to the addition of the PrEPsteps supplement questions (in September 2022) to inquire about their interest in completing the additional supplement questions.

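### The ingestion record compared between arms can be edited from participants' own records with no stated blinding to arm, while DBS, which edits cannot change, is not compared between arms

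*Combined protocol and SAP*

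**What the plan says.** The file prints the protocol text twice; the wording on this point is the same in both.

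- **Outcomes.** Section VII, Aim 2, will measure the association of PrEPsteps with percent adherence and with weeks of more than four doses. It does not say whether the edited or the unedited ingestion record is used.
- **Editing.** Section XI, Data Entry Process: "Ingestion data may potentially require editing if there are transmission failures, errors from the reader device, or manually recorded data from study participants". The vendor and the study team identify candidate edits together. "Edits to data will be agreed upon by both parties and approved by the PI". An audit trail is kept.
- **Transmission errors.** Section XI also provides for review of pill-to-Reader signalling for each participant: "If errors occur as a result of data transmission, we will correct" the adherence data.
- **Missing values.** "Each variable with missing data (such as an interruption between smartphone and sensor) will be identified and a placeholder" of -99 entered. Section VII does not say how such days enter either outcome.
- **What each arm is told.** Both arms get ingestion confirmations. Controls can query the app, and "Participants will receive weekly adherence metrics" applies to them as well as to the intervention arm. Both arms have "technology check-ins at days 2, 5, 7, 16, 19, 21" and reconciliation of discordant or nonadherent events with staff at visits. Corrective feedback, sent "2 hours after dosing window has closed without ingestion event", is listed for PrEPsteps only.
- **DBS.** The Section VI visit descriptions draw DBS tenofovir diphosphate in both arms at Visits 2, 3, 5 and 6. The only analysis planned for it in Section VII is validation of the ingestion data.

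**The concern.** One of the three grounds for an edit is the participant's own record, so self-report can enter an outcome that the background presents as objective. Section XI ties corrections for transmission errors to signal review. It gives no matching standard of evidence for edits that rest on a manual record.

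The people who identify and agree edits include the study team. Staff randomise participants at Visit 2, program LifeSteps responses for the PrEPsteps arm only, and run quality reviews separately by arm, so they can be expected to know allocation.

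The intervention itself creates extra occasions to notice and discuss an undetected dose. One is the same-day prompt. Another is the audio-recorded review of nonadherence episodes at Visit 5, which is listed for PrEPsteps only. If undetected doses are restored more often, or less often, in one arm, the adherence difference moves with no difference in pill taking. That difference is the pilot's quantitative evidence on potential for an effect (Aim 2). The measure that no edit can touch is collected in both arms but never compared between them.

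**Working it through.** The plan gives no power calculation, detection rate or SD, so there is no figure to reproduce. The check has three parts.

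**1. Shift in the between-arm difference**

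Inputs from the documents: 30 per arm (Aim 2); 90 days of pills after randomisation (30 dispensed at Visit 2 and 60 at Visit 3). The prompt may run for only the last 60 of those days, because the Study Visit 1 text times corrective feedback from Visit 3.

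Assumed inputs: true adherence a = 0.80 in both arms; a share f = 0.05 to 0.15 of taken doses undetected; SD of percent adherence 20 to 25 points.

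If a share r of undetected doses is restored, recorded adherence is a × (1 − f + f × r). With the same a and f in both arms, the false difference is a × f × (difference in r). For a 10-point difference in r:

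- f = 0.05: 0.80 × 0.05 × 0.10 = 0.4 points
- f = 0.15: 0.80 × 0.15 × 0.10 = 1.2 points
- If restoration differs only on 60 of 90 days, multiply by 60/90: 0.27 and 0.80 points

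Standard error of the difference = SD × √(2/30): 5.16 points (SD 20) or 6.45 points (SD 25).

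- Smallest ratio: 0.27 / 6.45 = 0.04 SE
- Largest ratio: 1.2 / 5.16 = 0.23 SE

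The shift is proportional to the gap in r. It is zero when r is equal, and its sign follows whichever arm has more doses restored. The documents give no basis for any particular gap.

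**2. Effect of the handling rule on the level in one arm**

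Same a and f:

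- Undetected doses counted as missed, a(1 − f): 76.0% and 68.0%
- Coded -99 and dropped, a(1 − f)/(1 − af): 0.76/0.96 = 79.2% and 0.68/0.88 = 77.3%
- Restored: 80%

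**3. What DBS can offer**

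With 30 per arm and complete samples, the 95% CI half-width for a between-arm mean difference is t(0.975, 58) × √(2/30) = 0.52 SD. Adjusted for the Visit 2 value with an assumed correlation of 0.5, it is t(0.975, 57) × √(2/30) × √(1 − 0.25) = 0.45 SD. Missed draws would widen both.

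Visit 6 has a separate interest. Participants are asked to bring all equipment back at Visit 5, and no later dispensing of study drug is described. A Visit 6 sample therefore has no concurrent ingestion record to validate, and the plan leaves it without a stated analysis. It would reflect PrEP taken after the study supply ended.

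**The case against.** **Safeguards exist.** Edits need two-party agreement and PI approval, with an audit trail. Signalling is reviewed for each participant. Section XI calls for pill counts at each study visit in both arms and for discrepancies to be addressed at the visit. Investigators run quality reviews in increments of 10 per arm, and the DSMB's remit includes data quality. This stands, and it rules out any suggestion that editing is uncontrolled. These safeguards still provide neither an arm-blind decision nor a by-arm report of edits.

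**Differential editing is hypothetical.** Both arms can notice an undetected dose, and no passage says that replies to the prompt feed into edits. This stands too. A reader might infer that edits will favour PrEPsteps; the documents do not support a direction. The prompt might lead a participant to report a taken dose, including through its free-text field, or to log a barrier for that dose instead.

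**The size could be overstated.** From part 2, a reader might infer a between-arm bias of 4 to 12 points (80 − 76.0 and 80 − 68.0). The documents do not support that. It is a shift in level that applies to either arm, and it supposes that every undetected dose is counted as missed. Section XI corrects transmission errors and codes identified interruptions as missing. For failures identified in that way, the spread is between dropping and restoring: 80 − 79.2 = 0.8 to 80 − 77.3 = 2.7 points.

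**A strict rule could backfire.** Allowing edits only on Reader or vendor logs would exclude taken doses that left no signal. If prompts change how often the Reader is used, that exclusion could itself differ by arm. This stands, and such a rule is not proposed here.

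**Unseen documents.** The nonadherence SOP and the message list were not available. The SOP is described as covering communication, so it may settle only part of this.

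**Conclusion.** The point holds as a risk with an inexpensive remedy. The record behind both between-arm outcomes may be edited from participants' manual records by people who can be expected to know arm, with no stated blinding. Only one arm is listed as being prompted after each undetected dose. The documents do not show that restoration differs.

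The possible shift is modest: 0.04 to 0.23 SE per 10-point restoration gap, in either direction. That rests on assumed 80% adherence, 5 to 15% of taken doses undetected and an SD of 20 to 25 points. The weeks outcome is open to the same shift but has not been sized separately.

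The unstated -99 rule and analysed record are missing detail and would not carry the point alone. The stronger reason to act is that DBS is already planned in both arms and would give a comparison that edits cannot affect. In a pilot of 30 per arm, the issue is how far the adherence signal can be trusted; no confirmatory test is at stake.

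**What to change.** 1. **Section VII, DBS.** Add a between-arm estimate with 95% CI of DBS tenofovir diphosphate at Visits 3, 5 and 6, adjusted for the Visit 2 value and labelled as unpowered. State that Visit 6 falls after the digital-pill period.
2. **Section XI, edits.** Have edits decided from study number only, without arm, using the same evidence in both arms (Reader or vendor logs and pill counts). Flag edits that rest only on a participant's manual record. Section X already identifies participants by study number on both dashboards. Because the NOMI dashboard also drives the intervention messages, the decision should be made from an extract without message history.
3. **Section VII, analysed record.** Compare arms on the corrected record. As sensitivity analyses, repeat the comparison on the unedited record and on the corrected record without manual-record edits. Handle -99 days by one stated rule in both arms. Tabulate edits and -99 days by arm from the existing audit trail.

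The cost is some text in Sections VII and XI, one table and a little more analysis, with no new visits, samples or participants. The downside is a secondary result that may be less favourable than the edited record.

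As a separate clerical correction, Section XI places DBS at Visits 3 and 4. Visit 4 is entirely remote, and the visit descriptions place DBS at Visits 2, 3, 5 and 6.
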